6.4.3.2 Secondary Objectives Analyses

Sperm parameters following ZyMot and density gradient sperm separation, as well as Euploid rates in the event that PGT-A was performed following ICSI comparing sperm separation with ZyMot to density gradient, will be assessed using the paired t-test, Wilcoxon signed rank test, or a generalized linear mixed model (GLMM). A random subject-specific intercept and an unstructured correlation structure will be used to account for within-subject correlation between rates between the two groups. Data will be reported as least squares means with corresponding 95% confidence intervals.

Pregnancy outcomes will be assessed using McNemar's test. The difference in good quality blastocyst development rate and pregnancy outcomes between the ZyMot and density gradient separation groups will also be analyzed separately using a conditional logistic regression model with generalized estimating equations to account for both correlation between observations from the same patient and the size of the cohort of eggs from each patient.

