- Following oocyte retrieval, oocytes will be denuded of their cumulus cells per standard protocol. If at least 6 mature oocytes (determined by visualization of a polar body) are present, half the oocytes will be ICSI inseminated with sperm prepared via ZyMot device and half will be ICSI inseminated with sperm prepared with density gradient. Patients whose patient identification number (PID) is even will have the group of oocytes inseminated with sperm separated via ZyMot device recorded first in the eMR gamete sheet (beginning with oocyte #1.) Patients with an odd PID will have the oocytes inseminated with sperm separated via density gradient recorded first in the eMR gamete sheet (beginning with oocyte #1.) In the event of an odd number of oocytes, the patients with even PIDs will have the extra oocyte inseminated with sperm separated via Zymot device and patients with odd PIDs will have the extra oocyte inseminated with sperm separated via density gradient. Inseminated oocytes will be grouped into separate wells of a LifeGlobal 4 well GPS dish (Cooper Surgical) by the sperm separation method — one well will contain all oocytes inseminated with sperm selected by ZyMot device and a separate well will contain all oocytes inseminated with sperm selected by density gradient centrifugation.

Control Group of Oocytes:

Half of the eggs will be inseminated via ICSI using sperm selected by conventional gradient centrifugation.

Treatment Group of Oocytes:

- Half of the eggs will be inseminated via ICSI using sperm selected using ZyMot.
- Fertilization assessment will be performed between 16 and 18 hours after insemination and normal fertilization will be considered visualization of exactly two pronuclei. Normally fertilized oocytes (embryos) will then be cultured in Continuous Single Culture Medium — NX Complete (Irvine Scientific) in separate, numbered droplets in LifeGlobal microdrop GPS dishes (Cooper Surgical.) The numbers of the droplets will correlate to oocyte/embryo number in the eMR gamete sheet and, thereby, also correlate to the type of sperm used for the insemination. Development of the embryos will be assessed on culture days 5 and 6 and embryo stage and grade will be recorded for each embryo.

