- Decision as to which embryo to transfer will be made by the clinical team irrespective of type of sperm preparation for insemination. Transfer of embryo is generally based on ploidy status (if PGT-A was performed) or blastocyst grade (if PGT-A was not performed). In the event that two embryos of similar quality are available for transfer, priority is given to lowest embryo number (correlated to oocyte/embryo number). The decision as to which embryo to transfer will be made regardless of whether the sperm used to inseminate the oocyte was processed with density gradient or ZyMot and will be as per our standard protocol.

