6.3.1 Study Schedule

Subject time devoted to this study will be the reviewing and signing the informed consent.

The timepoints for involvement in the study will be:

1. The process of informed consent for patient/sperm source dyads
2. The oocyte retrieval- After retrieval in the event that there are 6 or more mature oocytes, the couple will be enrolled into the study
3. The sperm separation- The sample will either be obtained via fresh production from sperm source the day of oocyte retrieval or will be cryopreserved sperm. The sample will be assessed the day of oocyte retrieval and if the sperm sample is sufficient, it will be processed via ZyMot and density gradient. Following processing of the sperm sample, in the event that there are 6 mature oocytes available to inseminate, the patient will be enrolled into the study. Oocytes will be randomized to insemination via density gradient separated sperm and ZyMot separated sperm.
4. In the event that the orders were written for ICSI per embryologist, if the patient does not meet criteria for IVF the day of oocyte retrieval (as per section 6.3), the oocytes will be inseminated via IVF with density separated sperm only, however, the pre and post sperm parameters following ZyMot separated sperm and density gradient separated sperm will be recorded as per our secondary objectives. Similarly, in the event that there are less than 6 mature oocytes, the oocytes will only be inseminated via density gradient separated sperm, however, pre and post sperm parameters following ZyMot separated sperm and density gradient separated sperm will be recorded as per our secondary objectives. Insemination- Following oocyte retrieval, those enrolled into the study will have their oocytes split and inseminated with ZyMot separated sperm and density gradient separated sperm.
5. Fertilization check- Approximately 16-18 hours following insemination the embryos will be assessed for fertilization.
6. Five and 6 days following insemination, the embryos will be assessed for stage of growth and those reaching blastocyst stage will be given a morphological grade.
7. In the event that patient will undergo a fresh transfer the patient will be transferred 5 days following oocyte retrieval. In the event that pre-implantation genetic testing is performed or the embryos are cryopreserved for any other reason, the patient may undergo a frozen embryo transfer in standard fashion.

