8. Nine days following embryo transfer, the patient will follow up for a pregnancy test. In the event its is positive, the patient will follow up approximately 2-3 days later for a repeat pregnancy test. Depending on the value, the patient will either follow up again for a pregnancy test or follow up approximately 1 week later for an ultrasound. In the event of a normal intrauterine pregnancy, the patient is generally referred to her Obstetrician for obstetric care.

As per our standard of care, patients will be contacted by embryology staff via phone after their expected due to date for their pregnancy outcome. Pregnancy outcomes will be recorded in the patient's medical record.

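### McNemar's test is planned for pregnancy outcomes, but nothing in the protocol gives a patient a transfer from each arm, so the required pair is undefined

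*Combined protocol and SAP*

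**What the plan says.** Section 6.4.3.2 names the test: "Pregnancy outcomes will be assessed using McNemar's test". It adds, for the same outcomes and for blastocyst development, a "conditional logistic regression model with generalized estimating equations to account for both correlation between observations from the same patient" and the number of eggs each patient contributes. Section 6.4.1 says only that analyses will be paired, without defining a pair.

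On what is transferred, section 6.1.2 says: "Decision as to which embryo to transfer will be made by the clinical team irrespective of type of sperm preparation for insemination". The choice generally rests on ploidy where PGT-A was done and on blastocyst grade otherwise. Ties follow a numbering rule: "In the event that two embryos of similar quality are available for transfer, priority is given to lowest embryo number". Numbering depends on the patient's identification number: "Patients whose patient identification number (PID) is even will have the group of oocytes inseminated with sperm separated via ZyMot device recorded first", and the reverse for odd numbers.

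On how many transfers there are, section 6.3.1 makes a fresh transfer conditional and says that, where embryos are frozen, "the patient may undergo a frozen embryo transfer in standard fashion". The outcome is then read at patient level: "Nine days following embryo transfer, the patient will follow up for a pregnancy test".

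**The concern.** McNemar's test compares two binary results from the same matched unit. Here the oocytes are allocated, while pregnancy is observed after a transfer that may involve either arm. The plan does not require a transfer from each arm, fix the number of transfers or of embryos per transfer, or say which transfers count.

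Three things follow:

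- Patients with transfers from one arm only are lost to the test.
- The patients who remain are selected. If a second transfer mostly follows a failed first one (an assumption), discordant pairs for live birth tend to count against the arm used first. This does not carry over to outcomes such as a clinical pregnancy that ends in miscarriage.
- The analyst would have to decide what constitutes a pair, possibly after seeing outcomes.

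The second model leaves the matter open. A conditional likelihood learns only from patients with both arms and discordant results, so it has the same limitation. A marginal GEE can use every patient. The text names both. At stake are the pregnancy, miscarriage and live birth comparisons.

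**Working it through.** **The plan's own figure.** The only sample size is for the primary endpoint (section 6.4.2): n = 16pq(1-r)/d², with p = (0.48 + 0.55)/2 = 0.515, q = 0.485, r = 0.5, d = 0.07. This gives 16 × 0.515 × 0.485 × 0.5 / 0.0049 = 407.8, rounded up to 408, which reproduces. No number of pairs or power is given for pregnancy outcomes.

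**Number of dyads.** Accrual ends at 408 oocytes. At the minimum of 6 per dyad, 408/6 = 68. At the average of 12 in section 5.3.1, 408/12 = 34.

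**What needs no assumption.** Zero pairs come from a patient with transfers from one arm only. When all m discordant pairs favour one arm, the exact two-sided p-value is 2 × 0.5^m: 0.0625 for m = 5 and 0.031 for m = 6. At least 6 discordant pairs are therefore needed.

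**Expected pairs.** The documents give no transfer outcomes, so the following is assumed: every dyad has a first transfer; live birth per transfer s is 30% to 60%; a second transfer follows only a failure; and a share w of failures, 20% to 100%, is followed by a transfer from the other arm. Then pairs = N(1-s)w and discordant pairs = N(1-s)w × s.

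| N | s | w | Pairs | Discordant | P(fewer than 6) |
|---|---|---|---|---|---|
| 34 | 0.3 | 0.2 | 4.8 | 1.4 | over 0.99 |
| 34 | 0.5 | 0.4 | 6.8 | 3.4 | 0.88 |
| 68 | 0.5 | 0.4 | 13.6 | 6.8 | 0.31 |
| 68 | 0.5 | 1.0 | 34.0 | 17.0 | under 0.001 |

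The last column is the binomial probability with N trials and success probability (1-s)ws. Over the assumed ranges, expected discordant pairs run from 1.4 to 17.0.

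**Direction and error rate.** Take N = 68, s = 0.5, w = 0.4 and equal true rates. If each arm goes first equally often, which the numbering rule would tend to produce, the 6.8 discordant pairs split 3.4 to 3.4 and the exact test rejects in 1.5% of trials. If one arm goes first in 60%, the split is 6.8 × 0.6 = 4.1 against 6.8 × 0.4 = 2.7, to the disadvantage of that arm, and the test rejects in about 3%. The false-positive rate is not inflated here. The trouble is few pairs, selected pairs and a possibly biased estimate.

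**Check of the alternative.** A simulation used 68 dyads, prognosis varying between patients as Beta(1,1) (assumed), every failed first transfer followed by a second, one arm first in 60%, and equal true rates. Pooling all transfers favoured the first-used arm by 1.2 percentage points when 40% of second transfers switched arm, and by about 3 points when all did. Using the first transfer only, the difference was about 0.1 point or less, which is simulation noise.

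**The case against.** The strongest reply is that the same paragraph already supplies a remedy. A model meant to handle correlation within a patient sounds like a patient-clustered GEE, which does not need both arms in each patient. That is a fair reading of the intent, but the model is also called conditional, and it is planned in addition to McNemar's test, not in its place.

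Section 5.3.1 also anticipates 138 patient cycles and up to 138 dyads. With N = 138, s = 0.5 and w = 0.4 there would be 27.6 pairs and 13.8 discordant, and fewer than 6 in only 0.5% of trials. But 138 dyads with at least 6 oocytes each means at least 828 oocytes, and the study ends at 408, so no more than 68 dyads can have split oocytes. Even with 138, the pair would be undefined.

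The illustrative figures are sensitive to assumption, and this stands. If prognosis varies as Beta(1,1), success after a failure is 1/3, so for N = 68 and w = 0.4 the expected discordant pairs fall from 6.8 to 4.5, and the chance of fewer than 6 rises from 31% to about 70%. If some dyads have no transfer, the counts fall further. The 60/40 split is likewise only an example.

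Finally, the protocol speaks of transferring an embryo in the singular, so transfers mixing both arms may be rare. The number per transfer is nevertheless not stated, and a pregnancy test could not attribute a mixed transfer to an arm.

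**Conclusion.** The concern holds. The planned test cannot be programmed for pregnancy outcomes without inventing a pair that the protocol does not define, and it discards every patient with transfers from one arm only. This follows from the text alone.

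The size of the loss depends on assumptions. Expected discordant pairs range from 1.4 to 17.0 for 34 to 68 dyads, against a minimum of 6 for any significant exact result. Pairs may arise by chance, because the protocol does not rule out transfers from both arms, but they would be a selected subset. The false-positive rate was not raised in the scenarios examined. The outcomes are secondary, and neither the primary analysis nor the 408-oocyte calculation depends on this. It should be corrected before pregnancy outcomes are analysed.

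**What to change.** In section 6.4.3.2, delete McNemar's test for pregnancy outcomes and remove the word *conditional* from the second model as applied to them. Then specify:

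- **Reporting:** each outcome per transfer, by arm of the transferred embryo, with any mixed-arm transfers listed separately.
- **Main comparison:** the first transfer per patient, in an ordinary logistic model with one record per patient and a 95% CI. Do not adjust for blastocyst grade, which arises after allocation and is part of the primary outcome.
- **Supportive:** all transfers, in a marginal logistic GEE clustered on patient, with a caution that pooling can favour the arm used first (1.2 to about 3 points in the check above).
- **Status:** descriptive, because the transferred embryo is selected after allocation on ploidy or grade.

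The cost is SAP wording plus recording the arm and order of each transferred embryo. Embryo number already links to arm under section 6.1.2. The pregnancy results would no longer carry a paired significance test. No change to clinical practice is involved.

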6.4.3.3 Safety/Pregnancy-related policy

Not applicable.

6.4.3.4 Analysis of Subject Characteristics

Subject characteristics will be documented including female age, male age, infertility diagnosis, stimulation protocol, medications used, gonadotropin dosage, method of trigger, infertility diagnosis, sperm parameters prior to sperm separation, gravity, parity, and previous pregnancy outcomes.

6.4.3.5 Interim Analysis

An interim analysis will be performed at the midway point of oocyte recruitment. Interim analysis will evaluate percentage of good quality embryo formation. Study will be terminated in the event that there is a significant decrease in good quality embryo formation in the study arm compared to the control arm.

6.4.3.6 Health economic evaluation

Not applicable.

6.4.3.7 Other

Not applicable.

6.4.4 Subsets and Covariates

This study will be randomizing sister oocytes (oocytes from the same patient within the same cycle) and thus limiting the impact of confounding variables.

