5.1 General Design Description

This study will be a randomized sister oocyte (oocytes from the same patient within the same cycle) study at a single academic institution. By randomizing sister oocytes, we will eliminate any potential confounding variables.

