6.4 Statistical Method

6.4.1 Statistical Design

All data will be de-identified and then will be analyzed by a statistician. Descriptive statistics of the study sample will be calculated (mean \pm standard deviation or median [25th, 75th percentiles] for continuous variables; frequency and percent for categorical data. Paired analyses will be performed. A result will be considered statistically significant at the $p < 0.05$ level of significance. All analyses will be performed using SAS version 9.4 (SAS Institute Inc., Cary, NC).

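### The protection from confounding claimed in 5.1 and 6.4.4 does not carry through to pregnancy outcomes, and no stated model includes female age if single-transfer patients are compared

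*Combined protocol and SAP*

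**What the plan says.** Section 6.4.4 is a single sentence: "This study will be randomizing sister oocytes (oocytes from the same patient within the same cycle) and thus limiting the impact of confounding variables". Section 5.1 goes further: "By randomizing sister oocytes, we will eliminate any potential confounding variables". Neither statement is restricted to a type of outcome, although 5.2.2 lists pregnancy, miscarriage and live birth among the secondary outcomes.

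Section 6.1.2 describes how the embryo is chosen: "Transfer of embryo is generally based on ploidy status (if PGT-A was performed) or blastocyst grade (if PGT-A was not performed". Between embryos of similar quality, the lowest embryo number has priority. Under 6.1.2 and 6.1.3, the parity of the patient identification number decides which arm holds the low numbers.

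On analysis, 6.4.1 says "Paired analyses will be performed". Section 6.4.3.2 says "Pregnancy outcomes will be assessed using McNemar's test" and adds a second analysis, a "conditional logistic regression model with generalized estimating equations". The stated purpose of this second model is that it should "account for both correlation between observations from the same patient and the size of the cohort of eggs from each patient". Section 6.4.3.4 says "Subject characteristics will be documented including female age, male age, infertility diagnosis", followed by further items. It gives these characteristics no role in any model.

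**The concern.** Splitting one patient's oocytes between arms balances everything about that patient for fertilisation and blastocyst formation. A pregnancy result belongs to the patient and follows a transfer, and transfers are not assigned. A patient with one single-embryo transfer contributes a result under one preparation and none under the other. Comparing such patients by arm is a comparison between patients, and the split of oocytes no longer holds age fixed.

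The written assurance that confounding is eliminated could lead readers to take any difference in pregnancy or live birth, or the lack of one, as a within-patient result. The plan also leaves the covariates for these outcomes open, so they might be chosen after the data are seen.

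**Working it through.** **1. What each named method does with a single-transfer patient**

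| Method (6.4.3.2) | Patient with a transfer from each arm | Patient with one single-embryo transfer |
|---|---|---|
| McNemar's test | Forms a pair; age held fixed | Not used |
| Logistic regression conditional on patient | Informative if the two results differ; age held fixed | Contributes nothing |
| Marginal logistic model fitted by GEE | Used, clustered | Used, compared with other patients; no age term stated |

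The second analysis named in 6.4.3.2 joins the last two rows, which are different approaches. Egg-cohort size is constant within a patient's cycle, so its main effect cancels when conditioning on that cycle. Listing it therefore fits the marginal reading somewhat better, but the text does not settle the matter. Nor does it say how a transfer with embryos from both arms is attributed.

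**2. How many transfers there could be**

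The plan's figure reproduces. With p = (0.48 + 0.55)/2 = 0.515, q = 0.485, r = 0.5 and d = 0.07, n = 16 × 0.515 × 0.485 × 0.5 / 0.07² = 407.8, so 408 oocytes. This covers blastocyst formation only; there is no calculation for pregnancy.

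At 6 oocytes per dyad, 408/6 = 68 dyads. At the average of 12 in 5.3.1, 408/12 = 34. Assuming one transfer per dyad, there are 34 to 68 transfers and no within-patient pairs.

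**3. Chance imbalance in age**

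Assumptions, not document figures: transfers split evenly between arms, half the patients older, a pregnancy rate lower by g = 15 to 25 points in the older half, and an overall rate near 50%.

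- The SD of the difference in the older share between arms is √(2 × 0.25/(n/2)) = √(1/n).
- The SD of the resulting shift in the arm difference is g × √(1/n).
- The SE of the arm difference at a 50% rate is also √(1/n).

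| Transfers | SE of arm difference | Shift SD, g = 15 | Shift SD, g = 25 |
|---|---|---|---|
| 34 | 17.1 points | 2.6 | 4.3 |
| 68 | 12.1 points | 1.8 | 3.0 |
| 138 | 8.5 points | 1.3 | 2.1 |

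The last row uses the 138 cycles also anticipated in 5.3.1. Age mix accounts for g² of the variance: 0.15² = 2% to 0.25² = 6%, whatever n is. Removing it would cut the SE by about 1 to 3%, since √(1 − 0.0225) = 0.989 and √(1 − 0.0625) = 0.968.

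With age as a continuous variable, the SE of the mean difference is √(4/n): 0.34 SD at 34 transfers and 0.24 SD at 68. The chance of an imbalance above 0.25 SD is 47% and 30% respectively.

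**4. Systematic imbalance**

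The transfer rule was simulated with no true device effect on pregnancy and an assumed age effect of −0.5 in log-odds per SD.

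- With no ZyMot effect on blastocysts, or a constant one (48% to 55%), mean age differed between arms by 0.00 to 0.03 SD and pregnancy rates by at most about 0.3 points.
- With a ZyMot effect varying with age (±0.28 log-odds per SD), the age difference reached 0.16 SD and the spurious pregnancy difference about 1.8 points.

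A separate simulation gave each dyad a latent blastocyst rate p, set pregnancy at 0.3 + 0.3p, and chose the transferred embryo at random among blastocysts. It gave 0.3 to 1.7 points against ZyMot through selection alone. Age is not in that model, so adjusting for age is not shown to remove this shift.

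**The case against.** A reader might infer that the plan compares pregnancy outcomes between transfers without adjusting for age. The documents do not say that. They specify paired methods, and both McNemar's test and a patient-conditional model hold age fixed for patients with transfers from both arms. Under those methods single-transfer patients drop out rather than confound. The unadjusted between-patient comparison arises only on the marginal GEE reading, or if the analysis is changed because pairs are lacking. This part of the objection stands.

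A reader might also infer that age biases the comparison systematically. Both arms exist in every patient, and ties follow identification-number parity, which has no evident link to age. Without an age-dependent device effect the bias is close to nil. The shifts of 2 to 4 points are chance, already inside the ordinary standard error. This also stands.

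Third, the documents give no number of transfers per patient, and 6.3.1 allows fresh and frozen transfers, so some pairs may exist. That is correct. But if a second transfer follows the failure of the first, the pair is confounded with transfer order, so pairing alone does not restore the protection claimed.

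None of this rescues the unrestricted statements in 5.1 and 6.4.4.

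**Conclusion.** The point holds in a limited form. The claims in 5.1 and 6.4.4 are sound for oocyte and embryo outcomes and unsupported for pregnancy outcomes. Female age is recorded but enters no stated model, which matters wherever single-transfer patients are analysed.

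The size is modest: under the assumed 15 to 25 point age gap, chance age mix is 2 to 6% of the variance of the arm difference. The documents support neither a finding of serious age bias nor a statement that the planned analysis is an unadjusted between-transfer comparison.

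These are secondary outcomes with no sample-size claim, and the primary analysis is unaffected. The change is worth considering rather than required. Its main value is to correct the assurance and fix the model in advance; the gain in precision is small.

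**What to change.** - In 5.1 and 6.4.4, limit the confounding statements to oocyte- and embryo-level outcomes.
- In 6.4.3.2, define the transfer unit for analysis (for example, each patient's first transfer) and state how a transfer with embryos from both arms is attributed.
- Analyse clinical pregnancy, ongoing pregnancy and live birth per transfer with a logistic model containing arm, female age (continuous) and PGT-A tested yes/no. Use GEE clustered on patient if repeat transfers are included. Do not adjust for embryo grade, which the sperm preparation may change.
- Label the comparison non-randomised and exploratory, and report rare outcomes such as ectopic pregnancy as counts.

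The cost is wording in the plan. Age is already recorded; PGT-A use is not listed in 6.4.3.4 but will be known from the euploidy outcome. The model gains two parameters with few events: at an assumed 45% pregnancy rate, 34 to 68 transfers give about 15 to 31 pregnancies, so the covariate list should stay this short. Adjustment does not remove selection at transfer, and the report should say so.
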